### 9.2.1 Galderma Chin Retrusion Scale (GCRS) Responders Rate

The responder rates based on GCRS as assessed by the BE (defined in [Section 3.2.2.1](#)) at Months 3, 6, 9 and 12 after last treatment will be presented by treatment group with their 95% CIs using the Clopper-Pearson method, and the two-sided p-value of the comparison of responder rates between the treatment groups at each visit using the Fisher's exact test. Results will include estimates of the responder rates, difference in responder rates, and corresponding 95% CIs, as well as a graph showing the responder rates for the two treatment groups over time. The difference in responder rates corresponding 95% CI will be generated using continuity-corrected confidence limits by specifying RISKDIFFC.

The number and percentage of subjects in each response category, from No Retrusion (0) to Severe Retrusion (3) of the BE's GCRS, will be summarized by visit for each treatment group. The number and percentage of subjects in each change from baseline bin (-3, -2, -1, 0, 1, 2, 3) will be summarized by visit for each treatment group.

The Treating Investigator's and the Blinded Evaluator's GCRS results, including the actual GCRS ratings, the change from Baseline and the BE responder status (yes/no), will be presented in a data listing.

GALDERMA

(S/N: 1581)

Title

43USCH2208 Statistical Analysis Plan (SAP)

Doc id

MA-60980

Effective date: 2024-05-29 18:37

Galderma

Protocol number: 43USCH2208

Protocol V4.0

Effective

Version: 1.0

Confidential

Statistical Analysis Plan Version #1.0

Page 36 of 63

GALDERMA

[figure not shown]
Title  
43USCH2208 Statistical Analysis Plan (SAP)

Doc id  
MA-60980

Galderma

Protocol number: 43USCH2208

Protocol V4.0

Effective

Effective date: 2024-05-29 18:37

Version: 1.0

Effective date: 2024-05-29 18:37

Galderma

Protocol number: 43USCH2208

Protocol V4.0

## 10.1 Study Drug Exposure

Data on extent of exposure and treatment procedure will be summarized by treatment group and by Injection Timepoint as defined in [section 4.5.2](#).

### 10.1.1 Injection Characteristics

Injection characteristics include injection administration, procedural anesthetics, and post-injection procedures used. No overall column will be included. The following parameters will be summarized by Injection Timepoint:

- Total number of subjects treated.
- Treatment Area (Sublabial Crease, Pogonium, Menton, Prejowl sulcus area – left hand side, Prejowl sulcus area – right hand side).
- Total number of syringes used.
- Injection tool(s) used by treatment area.
- Injection method(s) used.
- Depth(s) of injection (Deep, Supraperiosteal, other).
- Use of procedural anesthetics (yes/no).
- Type of anesthetics (Topical or local injection).
- Post-injection procedures (none, massage, ice pack, other).

Effective

Version: 1.0

Galderma

Protocol number: 43USCH2208

Protocol V4.0

**10.1.2 Injection Volume Administered**

The injection volume (mL) administered throughout the study will be presented descriptively by Injection Timepoints. No overall column will be included. Additionally, a cumulative sum will be presented adding Initial treatment and Touch-up.

All injection volume, injection characteristics, and post-injection procedures data will be presented by treatment and subject in a data listing for each visit with treatment. Procedural anesthetics will also be reported, specifying the anesthetic name, concentration, volume and type.

For the optional touch-up, the eligibility, and the reason for not performing the injection will also be presented by treatment and subject in a data listing.

**10.2 Adverse Events**

Adverse Event reporting on each subject will start once a subject is enrolled in the study. All other events that occur after the subject signs the ICF but before enrollment will be recorded in the subject's medical history. The reporting shall continue during each follow-up visit (including telephone contacts and extra visits between planned visits) until the last scheduled visit in the study.

All AEs reported will be listed, documenting the verbatim term, MedDRA Preferred Term (PT) and System Organ Class (SOC), affected area, event start and end date (or ongoing), seriousness (yes/no), intensity, relationship to study product (yes/no), relationship to injection procedure (yes/no), UADE status, AESI status, action taken, outcome, time to onset, duration and Injection Timepoint. All AE endpoints will be presented Overall. The Overall Summary of Adverse Events table and the Adverse Events by System Organ Class and Preferred Term table will be presented Overall and by Injection Timepoint in which they occurred (see definition in [Section 4.5.2](#)). Additional presentations of AE endpoints may be presented by Injection Timepoint on an as needed basis.

Only AEs occurring after treatment will be included in analysis. AEs occurring before initial treatment, if any, will only be presented in data listings. Missing dates, intensity, relationship, and seriousness will be imputed as described in [Section 11.1](#) and [Section 11.2](#).

**10.2.1 Summary of Adverse Events**

A summary of AEs will be provided, which will include the number and percentage of subjects and number of events in the following categories:

- Any AE.
- Any AE related to study product or injection procedure.
- Any AE unrelated to study product or injection procedure.
- Any serious AE.
- Any serious AE related to study product or injection procedure.

Confidential

Statistical Analysis Plan Version #1.0

Page 39 of 63

Effective date: 2024-05-29 18:37

Effective

Version: 1.0

Galderma

Protocol number: 43USCH2208

Protocol V4.0

- Any serious AE unrelated to study product or injection procedure.
- Any AE leading to study discontinuation.
- Any AE ongoing at the end of the study.
- Any AESI
- Any UADE
- Subjects who did not have any AE.

The number and percentage of subjects with at least one AE and the number of events will be summarized by SOC and PT. System Organ Classes and PTs will be sorted in descending frequency first (by Restylane Lyft with Lidocaine group) and then alphabetically if there are ties. This sorting method will apply to all other AE tables described below.

### 10.2.2 Intensity of the Adverse Events

The intensity of the AEs (mild, moderate, or severe) will be recorded. If the intensity changes within one day, the maximum intensity of the AE during that day will be recorded. If the intensity assessment is missing, the intensity of 'Severe' will be assumed. AEs will be summarized by SOC, PT and intensity. If a subject has multiple occurrences of the same MedDRA SOC or PT, then only the most severe event will be summarized in the tables for that SOC and PT.

### 10.2.3 Relationship to Study Product of Injection Procedure

Each AE will be assessed by the Investigator for a reasonable possibility of a causal relationship with the study product and with its use (the injection procedure), both on a two-point scale (Yes or No). If the response to any of the questions "*Do you consider that there is a reasonable possibility that the event may have been caused by the study product?*" or "*Do you consider that there is a reasonable possibility that the event may have been caused by the study product injection procedure?*" is "Yes", then an AE is considered related for the analysis. Missing relationships will be considered related.

Related AEs will be summarized by SOC, PT and maximum intensity (defined in [Section 10.2.2](#)). Unrelated AEs, as well as serious related AEs, will also each be summarized by SOC, PT and maximum intensity. If a subject has multiple occurrences of the same MedDRA SOC or PT, then only the most severe event will be summarized in the tables for that SOC and PT.

Finally, the number of subjects with related AEs will be summarized by SOC, PT, and action taken (none, medication treatment, non-pharmacological treatment, other procedures/tests, subject withdrawn). Subjects will be only counted in 'None' category if no other action was taken.

### 10.2.4 Time to Onset and Duration of AEs

Time to onset and duration of related AEs will be recorded. Time to onset of an AE will be derived as the AE start date minus the date of most recent prior treatment. If the AE start

Effective date: 2024-05-29 18:37

Effective

Version: 1.0

Galderma

Protocol number: 43USCH2208

Protocol V4.0

date is partially/completely missing, it will be imputed using the imputation rules specified in [Section 11.2](#).

Duration of an AE will be derived as the AE stop date minus the AE start date + 1. If the AE start date is partially/completely missing, it will be imputed using the imputation rules specified in [Section 11.2](#). A completely missing AE stop date will not be imputed and therefore no duration will be calculated in these cases.

The number of days to onset and the duration of each respective related AEs will be summarized by SOC and PT using the mean, SD, min, max and median. These summaries are at the event level so that subjects will be counted once for each multiple related AE they experience. Related AEs with onset >21 days after the most recent treatment will be listed.

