7.9.7 Follow-up of adverse events

7.9.7.1 Follow-up of unresolved events ongoing at termination of the study

All serious as well as non-serious AEs with a probable, possible, or causal relationship to the study product or treatment procedure and ongoing at study end/or ongoing when a subject terminates the study participation early/or ongoing if the study is temporarily halted, shall be followed up after the subject's participation in the study is over.

Version: 4.0

Effective date: 2023-05-24 22:48

Such events shall be followed-up until resolved, assessed as chronic or stable, or subject is lost to follow-up. Final outcome after the end of the study shall be reported on the AE Follow-up form.

Other AEs will be monitored until the last visit if they have not resolved or reached a stable condition.

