**Table 8. Imputation Criteria for Missing/Partial Dates**

| Variable                            | Missing Day  | Missing Month or Day and Month   | Missing Year, Month and Year, or Day and Year   | Missing Day, Month, Year                        |
|-------------------------------------|--|--|---|---|
| Adverse Event/Medication Start Date | Assign to the first of the month (i.e., UNK-JAN-2023 becomes 01-JAN-2023)  | Assign to the month of ‘June’ (i.e., 01-UNK-2023 becomes 01-JUN-2023), provided the imputed date is on or after the subject’s Baseline study treatment date; otherwise, the subsequent month after study treatment will be used. | Assign to year of Baseline study treatment (i.e., 01-JAN-UNK becomes 01-JAN-2019), provided the imputed date is on or after the subject’s study treatment date; otherwise, the date of Baseline study treatment will be used. | Assign to Baseline study treatment date         |
| Adverse Event/Medication End Date   | Assign the last day of the month (i.e., UNK-JAN-2023 becomes 31-JAN-2023). | Assign to the subsequent month after the start date.   | Assign to the year of Baseline study treatment (i.e., 01-JAN-UNK becomes 01-JAN-2023), provided the imputed date is after the start date; otherwise, the subsequent year after start date will be used.                       | Assumed AE/medication is ongoing; no imputation |

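### Related-AE duration is summarised only over events with a full or partly imputed stop date, so the mean and maximum run low if some related AEs are unresolved

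*SAP*

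**What the plan says.** SAP 10.2.4 defines the quantity: "Duration of an AE will be derived as the AE stop date minus the AE start date + 1". For an event with no stop date at all, the rule is: "A completely missing AE stop date will not be imputed and therefore no duration will be calculated in these cases". SAP 11.2, Table 8, gives the meaning of that blank for an end date: "Assumed AE/medication is ongoing; no imputation". A partly missing end date is treated differently. Table 8 fills it in (a missing day, for example, becomes the last day of the month), so such an event does get a duration.

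The durations of related AEs "will be summarized by SOC and PT using the mean, SD, min, max and median", at event level. The section specifies no censoring, no count of excluded events and no label restricting the table to events that ended.

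Ongoing events are reported elsewhere. SAP 10.2.1 has a summary line for "Any AE ongoing at the end of the study", and the listing in SAP 10.2 flags an event as ongoing where there is no end date. Protocol 7.9.7.1 requires follow-up of related AEs still open when participation ends: "Such events shall be followed-up until resolved, assessed as chronic or stable, or subject is lost to follow-up".

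**The concern.** The exclusion depends on the outcome being measured. By the SAP's own reading, an event without a stop date is one that has not finished. Leaving it out removes the events most likely to be long and keeps those that ended within follow-up.

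Duration is an informative part of a filler's safety profile. Protocol 1.3 names mass/induration among the most common post-marketing complaints in the chin, and Protocol 5.3.3 says common injection reactions typically resolve within two to four weeks. A duration table is a natural place to check that expectation, yet it omits the events that would contradict it. If the arms differ in their share of unresolved related events, the understatement differs between arms too.

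The rule also sits oddly beside the SAP's other conventions. SAP 11.1 assigns the most severe value to missing AE intensity, relationship or seriousness. SAP 3.2.4.9 gives detailed censoring rules for time to social engagement. Neither approach is carried over to AE duration.

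**Working it through.** **Plan's own figure.** The documents state no AE duration and no expected share of ongoing events, so there is nothing to reproduce. Only the direction of the bias can be derived. Its size can only be illustrated.

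**Direction.** Let T be an event's true duration, with distribution function F, and C the follow-up available after onset, independent of T. The table uses only events with T ≤ C. For any t and any c, F(min(t, c)) ≥ F(t)·F(c). Averaging over C gives P(T ≤ t | T ≤ C) = E[F(min(t, C))] / E[F(C)] ≥ F(t). Completed events are therefore stochastically no longer than all events, and their mean and median cannot exceed the true values.

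**Hand illustration (all inputs assumed).** Suppose resolved events average 14 days and ongoing events have run 330 days. That fits within the 48 × 7 = 336 days of follow-up after last treatment (SAP 3.2).
- Planned table: mean 14 days.
- 10% ongoing, counted only to date: 0.90 × 14 + 0.10 × 330 = 12.6 + 33.0 = 45.6 days, a lower bound.
- 5% ongoing: 0.95 × 14 + 0.05 × 330 = 13.3 + 16.5 = 29.8 days, a lower bound.
- Median, if resolved durations are exponential: 14 × ln 2 = 9.7 days in the planned table. With 10% ongoing, solve 0.90 × (1 − exp(−t/14)) = 0.5, giving t = 11.4 days. With 5% ongoing, t = 10.5 days.

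**Simulation (all inputs assumed except the 336 days).** There were 200,000 events. Short events were exponential with mean 10 days, and a stated share of long events was exponential with mean 180 or 365 days. Onset was uniform over days 0–28 (early) or days 0–336 (spread). The Kaplan-Meier median used 20,000 of the events.

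| Long share | Long mean (days) | Onset | Ongoing at end | True mean / median | Completed-only mean / median | Kaplan-Meier median |
|---|---|---|---|---|---|---|
| 0% | – | early | 0.0% | 10.0 / 6.9 | 10.0 / 6.9 | 6.9 |
| 0% | – | spread | 2.9–3.0% | 10.0 / 6.9 | 9.7 / 6.7 | 6.9–7.0 |
| 10% | 180 | early | 1.6% | 26.9 / 8.0 | 19.1 / 7.8 | 8.0 |
| 10% | 180 | spread | 7.2% | 26.8 / 8.0 | 13.9 / 7.3 | 8.2 |
| 10% | 365 | early | 4.1% | 45.5 / 8.1 | 17.9 / 7.6 | 8.1 |
| 10% | 365 | spread | 9.3% | 45.5 / 8.0 | 12.9 / 7.0 | 7.9 |
| 30% | 180 | early | 5.0% | 60.6 / 11.6 | 37.5 / 10.5 | 11.5 |
| 30% | 365 | spread | 21.7% | 116.2 / 12.0 | 21.2 / 8.1 | 12.0 |

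With 10% long events, the mean falls by between 1 − 19.1/26.9 = 29% and 1 − 12.9/45.5 = 72%. The median falls by between 1 − 7.8/8.0 = 2.5% and 1 − 7.0/8.0 = 12.5%. In the last row the median falls by 1 − 8.1/12.0 = 32.5%. The Kaplan-Meier median stays close to the true value throughout.

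**Maximum.** Take ten events: eight resolved at 5, 7, 10, 14, 14, 21, 28 and 60 days, and two ongoing at 300 and 330 days. The planned table shows mean 159/8 = 19.9, median 14 and maximum 60. Counting the ongoing events to date gives mean 789/10 = 78.9, median 17.5 and maximum at least 330.

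**The case against.** The strongest reply is that the plan already shows ongoing events in several places.
- SAP 10.2.1 counts subjects and events ongoing at study end, and SAP 4 puts summaries in columns by treatment.
- Ongoing related AEs stay in the SOC, PT and intensity tables of SAP 10.2.3.
- Palpability is assessed at every physical visit and tabulated by visit (SAP 10.6), which bears on persistent lumps.
- SAP 11.1 has missing values reported as appropriate in all outputs, SAP 4 includes n for continuous endpoints, and the table shells are in a separate document. A count of missing durations may therefore appear.

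This largely stands, and it rules out the inference that ongoing AEs vanish from the safety report. It does not repair the duration table. The ongoing count covers all AEs, not only related ones, and is not broken down by PT. A count of missing durations would show that events were excluded but would not correct the mean, median or maximum.

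A reader might also infer that events judged chronic or stable never receive a stop date. That is plausible, since Protocol 7.9.8 defines the stop date as the last symptomatic day, but no document says it. Follow-up under Protocol 7.9.7.1 may supply later stop dates for some events. The SAP does not say whether those dates enter the analysis.

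Finally, it is fair to object that any magnitude rests on assumed inputs and that the median, reported beside the mean, is much less affected.

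**Conclusion.** The point holds as a minor one, confined to one descriptive safety table. The stated rule makes the mean and maximum of related-AE duration too low whenever some related AEs are unresolved. The median is affected modestly when the share of long events is small, and more when it is large. If nearly all events resolve, the bias is negligible.

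The direction rests on two assumptions: that a blank stop date means an ongoing event, as Table 8 says, and that duration is independent of available follow-up. Stop dates missing purely at random would cause no bias. Filling in missing days tends to lengthen duration (start to the first of the month, end to the last), but only for the events concerned.

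The illustrative figures, such as 14 days against 45.6, should not be read as estimates for this trial. Nor do the documents show that the arms will differ in unresolved events. The primary test and the sample size are unaffected.

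**What to change.** Make three changes to SAP 10.2.4:
1. Add a Kaplan-Meier summary of related-AE duration by treatment, overall and for frequent PTs, with ongoing events censored at last contact.
2. Label the existing mean/median/maximum table 'events with a stop date only'.
3. Show the number of ongoing related events excluded beside each SOC/PT entry, by treatment.

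The same paragraph should say whether stop dates recorded on the AE Follow-up form after study end are used.

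No new data are needed, because start dates, ongoing status and visit dates are already collected. The cost is one SAP paragraph and a little more analysis work. The Kaplan-Meier median may not be reached for rare PTs, and any confidence intervals would need to allow for repeated events within a subject. If the extra analysis is unwelcome, the label and the counts alone would stop the table from being misread, though they would not remove the bias.

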### 10.2.5 Adverse Events of Special Interest

For this study, all instances of visual disturbances, regardless of relationship to study product or seriousness are considered AESIs and are outlined in the protocol.

In addition, the following events are considered AESIs:

- All abnormal findings in functionality tests, assessed by the Investigator, regardless of relationship to the study product or seriousness
- Stroke
- Skin necrosis

AESIs, as identified in the EDC, will be summarized the same way as AEs, by SOC and PT, and will be presented in a listing.

### 10.2.6 Death, Serious Adverse Events, Adverse Events Leading to Discontinuation of Study

Serious AEs, AEs resulting in death on study and AEs leading to discontinuation of study will be reported in separate listings. These listings will include the same variables as the listing for all AEs, and the Serious Adverse Events (SAEs) listing will additionally include the SAE criteria.

## 10.3 Subject pain assessment

The Numeric Pain Scale (NPS) will be treated as a continuous variable and will be summarized descriptively by visit, timepoint (pre- and post-injection). The change from pre- to post-injection pain will also be presented.

Subject pain assessment will also be presented in a data listing that will include the reason why the assessment was not done, if applicable.

Galderma

Protocol number: 43USCH2208

Protocol V4.0

#### 10.4 Sensory tests

Sensory tests, consisting of the Monofilament Test and the Cotton Wisp Test, will be summarized with counts and percentages of subjects with normal/abnormal findings by visit.

The sensory test will be presented in a data listing that will include the assessments of sensation at all locations for both tests, including the final test scores. When an abnormality is identified, the description of this abnormality will appear in the listing.

#### 10.5 Functionality tests

Lip Movement - Word Pronunciation, will be described with counts and percentages for each word and the word score will be presented using mean, SD, minimum, maximum, and median statistics by visit. Functionality tests, consisting of the Lip Function - Drinking from Straw and Chin Function - Open and Close Mouth, will be summarized with counts and percentages of subjects with normal/abnormal findings by visit.

The functionality test will be presented in a data listing that will include the assessments of lip movement and the lip and chin function. When an abnormality is identified, the description of this abnormality will appear in the listing.

#### 10.6 Assessment of palpability

Palpation data will be summarized with counts and percentages of subjects in each category (Yes – Expected Feel (Normal), Yes – Unexpected Feel (Abnormal)) by visit.

The palpation data will be presented in a data listing that will include the description of abnormality when it applies and the reason why the assessment was not done when it applies.

#### 10.7 Changes in hair growth

Changes in hair growth data will be summarized with counts and percentages of subjects in each category (Yes, No) by visit.

The changes in hair growth data will be presented in a data listing that will include the description of abnormality when it applies.

#### 10.8 Visual Function Assessments

##### 10.8.1 Snellen Visual Acuity

The number and percentage of subjects that experience an Acute, Compared to Previous Visit, and/or Change from Baseline worsening of 1+ line change in at least one eye during the study will be summarized by eye, visit and timepoint (pre- or post-injection, if

Effective date: 2024-05-29 18:37

Effective

Version: 1.0

Galderma

Protocol number: 43USCH2208

Protocol V4.0

applicable). The number of subjects with a non-missing Snellen assessment at a respective visit/timepoint will be used as the denominator.

Snellen VA Line Changes will be presented by eye in an (a, b) format, where a represents the individual change in the left eye and b represents the individual change in the right eye (e.g., (-2, -1) indicates a 2-line worsening in the left eye and a 1-line worsening in the right eye).

Snellen Visual Acuity test data will be presented in a listing.

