7.6 Visual function assessment

Visual function assessments will be performed at screening, baseline and at all physical follow-up visits. At the treatment visits, the visual function assessment tests will be performed prior to and approximately 30 minutes post injection of the study product. These assessments include Snellen visual acuity, extraocular muscle function, and confrontation visual field tests.

The subject is considered to have normal or acceptable visual acuity if the Investigator can adequately measure the quality of his/her eyesight using the Snellen Eye Chart. If the subject is found to have severely impaired/absent eye function (20/50 or worse) in one or both eyes, even with the use of prescribed corrective lenses, and/or any other condition with the potential to cause a decline of visual acuity, s/he will be considered to have abnormal vision and will not be eligible for enrollment.

All worsening of vision during the study (for visual acuity compared to baseline and post injection compared to pre injection at treatment visits) should be assessed by the Investigator **as an adverse event of special interest (AESI)** per Section 7.10. If the subject experiences clinically significant changes in vision, the Investigator should consider further assessment and treatment by an eye specialist (ophthalmologist or retinal specialist). The Investigator should conduct appropriate follow-up with the subject to determine the cause, intensity, seriousness, relationship to the study product or procedures, and outcome.

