### 3.2 Overall Design

This is a prospective, randomized, evaluator-blinded, parallel group, comparator-controlled, multicenter study in the US to evaluate the safety and effectiveness of Restylane Lyft with Lidocaine for augmentation of the chin region to improve the chin profile. The chin region is comprised of the anatomical areas of the pogonion, menton, and pre-jowl sulcus. Before the study starts, a randomization list will be prepared under the supervision of a designated biostatistician from the Sponsor.

Injection technique is at the Treating Investigator's discretion with needle only or a combination of needle and cannula. Restylane Lyft with Lidocaine and the comparator-

Version: 1.0

Effective

Galderma

Protocol number: 43USCH2208

Protocol V4.0

control will be administered by needle in the pogonion. The mentum and pre-jowl sulci may be injected by needle or cannula.

At least 35 subjects will be Fitzpatrick skin type (FST) IV through VI, this includes at least 18 subjects with FST V – VI, where at least 9 subjects will be FST V and at least 9 subjects will be FST VI.

After providing informed consent, eligible subjects randomized to receive either Restylane Lyft with Lidocaine or a comparator-control will be injected by the Treating Investigator at Baseline (Day 1). A follow-up telephone call should be made 72 hours after treatment and a follow-up visit should be scheduled after 14 days.

Optional touch-up treatment may be administered 1 month (4 weeks) after initial treatment, if deemed necessary by the Treating Investigator and the subject to obtain optimal aesthetic improvement. If optional touch-up is performed, a 72-hour follow-up telephone call, a follow-up visit at 14 days, and a follow-up visit at 1 month should be scheduled.

Appropriate injection volume for the chin area will be determined by the Treating Investigator but is not to exceed a maximum total volume of 4.0 mL for initial and touch-up treatments combined. Injection in the pogonion is only permitted with a needle. Both needle and cannula are permitted for injection in the other treatment areas.

Investigator blinding will be accomplished by using a Treating Investigator to administer the treatments and a Blinded Evaluator, to whom randomization and treatment are concealed, to conduct the blinded assessments. Safety assessments will be performed by non-blinded personnel.

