**3.2.5.6 Visual Function Assessment**

Three visual function assessments will be performed at screening, baseline and at all physical follow-up visits. At the treatment visits, the visual function assessment tests will be performed prior to and approximately 30 minutes post injection of the study product.

|   |  |                                   |
|---|--|-----------------------------------|
| 
GALDERMA
<small>EST. 1981</small>
 | 
Title
43USCH2208 Statistical Analysis Plan (SAP)
 | 
Doc id
MA-60980
 |
|---|--|-----------------------------------|

Effective date: 2024-05-29 18:37

Effective

Version: 1.0

Galderma

Protocol number: 43USCH2208

Protocol V4.0

The sections below provide descriptions of the visual function assessments that will be performed.

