#### 3.2.5.6.1 Snellen Visual Acuity

A Snellen eye chart will be used to objectively assess visual acuity for distance vision. Visual acuity will be conducted using the subject's best distance correction (e.g., contacts or eyeglasses) at a distance of 6 feet from the chart. Each eye will be measured separately by either using an occluder or having the subject cover each eye. The subject will be asked to start reading the letters at the top of the chart working their way to the bottom. The smallest row of letters that the subject can read will indicate their visual acuity listed on the chart. Any subject requiring vision acuity correction must be assessed using the prescribed correction (e.g., contacts or eyeglasses).

Unacceptable vision for a subject to be eligible for enrollment would be an absolute score on the Snellen eye chart 20/50 or worse in one or both eyes.

A 1+ worsening line change in Snellen Visual Acuity (VA) is when a subject moves up at least one line of letters on the Snellen Eye Chart (Figure 1). For example, if a subject's VA at baseline is 20/40 for the left and right eyes and then at Visit 1d is 20/70 for the left eye and 20/50 in the right eye, the subject experienced a 2-line worsening for the left eye and a 1-line worsening in the right eye.

Figure 1: Snellen Eye Chart

Galderma

Protocol number: 43USCH2208

Protocol V4.0

Given that VA is assessed at every study visit (pre-and-post treatment for applicable visits), there are many ways to assess a 1+ worsening line change:

- Acute worsening – A 1+ worsening line change between the pre-treatment and post-treatment VA, for visits where an injection is given.
- Compared to Previous visit – A 1+ worsening line change between the current visit VA and the previous visit VA (e.g., Visit 4 VA compared to Visit 3 VA). If the 'previous' visit has both pre-and-post treatment VA values, the post-treatment VA will be used; if the 'current' visit has both pre-and-post treatment VA values, both VAs will be compared to the 'previous' visit VA.
- Change from Baseline – A 1+ worsening line change between a post-baseline visit VA and Baseline (pre-treatment) VA. For post-baseline visits with both pre-and-post treatment VA, both will be compared to the Baseline (pre-treatment) VA.

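### The Snellen worsening denominators do not require the comparator reading, which slightly understates the percentages, mainly for the comparison with the previous visit

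*SAP*

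**What the plan says.** SAP 3.2.5.6.1 defines three outcomes:

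- The first, called acute, is a loss of at least one line from before to after the injection, and exists only at visits with treatment.
- The second looks back one visit: "A 1+ worsening line change between the current visit VA and the previous visit VA". Where the subject was treated at the current visit, its two readings are each set against the earlier one.
- The third is measured from the start of the study: "A 1+ worsening line change between a post-baseline visit VA and Baseline (pre-treatment) VA".

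SAP 10.8.1 tabulates subjects with each kind of worsening separately for each eye, each visit and each timepoint, the timepoint being before or after injection. Its denominator rule is: "The number of subjects with a non-missing Snellen assessment at a respective visit/timepoint will be used as the denominator". Neither section says what happens when the comparator reading is missing.

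Three further points fix who has which reading:

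- **Schedule.** Protocol 7.6 states: "Visual function assessments will be performed at screening, baseline and at all physical follow-up visits". According to SAP 3.2.5.6, subjects who are injected are tested twice that day, once beforehand and once about half an hour later.
- **Touch-up.** SAP 3.2 makes it optional: "Optional touch-up treatment may be administered 1 month (4 weeks) after initial treatment, if deemed necessary by the Treating Investigator". The subject takes part in that decision. No expected touch-up rate is given.
- **Screening and baseline.** Protocol 3.4 and 8.2 allow both visits on one day. Protocol 8.2 asks for the visual tests to be repeated at baseline only when the days differ.

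**The concern.** The numerator needs two readings and the denominator needs one. A subject with a current reading but no comparator cannot enter the numerator, yet is counted in the denominator and so is treated as not worsened. The error runs in one direction only: it lowers the reported percentage.

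Vision is a prominent safety topic in this trial. Protocol 7.6.1 and 7.10 make a loss of one line or more, from baseline or from pre- to post-injection, an adverse event of special interest. The summary percentages should therefore rest on subjects in whom worsening could have been observed. What is at stake is the accuracy of some descriptive percentages. Detection of events and the trial's conclusions are not affected.

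**Working it through.** **Plan figures.** The plan states no Snellen rate, touch-up rate, missing-reading rate or share of combined visits, so there is no Snellen figure to reproduce. The sample size only sets the scale. With SD 0.7, margin 0.5, true difference 0.1, 90% power, one-sided 0.025 and 2:1 allocation, the control arm needs 1.5 × (0.7 × (1.960 + 1.282) / 0.4)² = 48.3, so 49, and 49 × 3 = 147 evaluable, as stated. Then 147 / 0.85 = 173, against the stated approximate 174 (116 and 58).

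**Formula.** Let *m* be the share of subjects with a current reading who have no comparator. If *x* subjects worsened among *N* with a current reading, the SAP reports *x*/*N*. The percentage among comparable subjects is *x*/(*N*(1 − *m*)). The understatement factor is 1/(1 − *m*), whatever *x* and *N* are.

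**Compared to previous visit, after a missed visit** (*m* assumed, and assuming that no earlier visit is substituted):

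| *m* | 1/(1 − *m*) |
|---|---|
| 5% | 1.05 |
| 10% | 1.11 |
| 15% | 1.18 |

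For scale, take 3 worsened subjects (assumed) among 116 with a current reading. The reported figure is 3/116 = 2.6%. With 15% lacking the previous reading, 116 × 0.85 ≈ 99 are comparable, and 3/99 = 3.0%.

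**Compared to previous visit, at Visit 1b.** The previous visit here is screening. If screening and baseline are combined and no separate earlier reading exists, *m* is the share of combined visits. Assumed shares of 25%, 50% and 75% give 1/0.75 = 1.33, 1/0.50 = 2.0 and 1/0.25 = 4.0. This applies only if the comparison is tabulated at Visit 1b, which the SAP does not exclude, and only if one reading is not entered for both visits, on which the SAP is silent.

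**Acute worsening.** The table is split by timepoint, and the outcome exists only where an injection is given, so it belongs to the post-injection timepoint. At Visit 3 only subjects who received the touch-up have a post-injection reading, and the schedule requires a pre-injection test at the same visit. Here *m* is the share of injected subjects whose pre-injection test was missed: 0%, 2% and 5% give 1.00, 1.02 and 1.05. Even an assumed 10% gives only 1.11.

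**Change from Baseline.** Acuity is an eligibility test (Protocol 7.6), and SAP 4.4 takes the latest measurement before first treatment, unscheduled visits included. *m* should be near zero and the factor close to 1.00.

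**The case against.** The strongest reply is that the gap has little practical consequence, and most of that reply stands.

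- **Small where it matters most.** Protocol 7.10 names the changes from baseline and from pre- to post-injection as events of special interest. These are the two comparisons that are barely affected.
- **No event is hidden.** Protocol 7.13.1 requires such events to be reported to the sponsor within 24 hours. SAP 10.2.5 summarises and lists them. SAP 10.8.1 itself gives counts, line changes by eye and a full listing. No test or decision rule uses the percentage.
- **Observed cases.** SAP 11.1 describes safety data on observed cases, and a change with one reading missing is not an observed change. This favours a both-readings interpretation, but 10.8.1 states its own denominator explicitly, and a programmer would follow that sentence.
- **Visit 1b.** The larger factors rest on assumed shares. The post-injection reading there is in any case also compared with the pre-injection reading.

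A reader might go the other way and infer that acute worsening after touch-up is understated severalfold. Counting all 116 subjects at Visit 3 when an assumed 30% (35) were injected would give 3/116 = 2.6% instead of 3/35 = 8.6%. Over assumed touch-up rates of 20% to 80% the factor would run from 5.0 down to 1.25, and it would differ between arms if touch-up use differed. This requires dropping the timepoint from the rule. SAP 10.8.1 names the timepoint both in the tabulation and in the denominator, so subjects not injected fall outside the post-injection denominator. The text supports neither the severalfold dilution nor the arm distortion. At most, the slash between visit and timepoint leaves slight room for misprogramming.

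**Conclusion.** The point holds as a minor defect. The stated rule leaves subjects without a comparator in the denominator, and the percentage can only be biased downward. The effect falls mainly on the previous-visit comparison: a factor of about 1.05 to 1.18 if 5% to 15% lack the previous reading, and possibly more at Visit 1b if visits are combined and no separate earlier reading exists. For acute worsening and change from Baseline it is about nil to a few percent. All missing-reading and combined-visit shares are assumptions. The formula and the direction of the error do not depend on them.

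**What to change.** Replace the denominator sentence in SAP 10.8.1 with:

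> For each outcome the denominator is the number of subjects with both readings needed for that comparison (acute: pre- and post-injection readings at that treatment visit; previous visit: current and previous reading; Baseline: current and Baseline reading).

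This also makes explicit that acute worsening at Visit 3 is reported only in subjects who received the touch-up, and so removes any room for a visit-only denominator.

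The cost is one sentence and a denominator flag in the program. No data collection changes. Some reported percentages become slightly less favourable, and denominators will differ between the three outcomes at the same visit, so the tables should show them.
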